11.3 Cumulative failure time approach

Below, we first describe our general approach for estimating the cumulative incidence parameter, and we subsequently provide details describing how this approach is applied for each of the contrasts of interest.

We estimate the marginalized cumulative incidence function $\Gamma^a(t) = E_W[P(T \leq t | A = a, W)]$ using the strategy proposed by Westling et al. (2023). Estimating the marginalized cumulative incidence function requires estimation of the following three nuisance functions:

1. The conditional probability of the outcome by or prior to time t , given analysis group and covariates, $\eta_1(t, a, w) = P(T \leq t | A = a, W = w)$
2. The conditional probability of censoring by or prior to time t , given analysis group and covariates, $\eta_2(t, a, w) = P(C \leq t | A = a, W)$ (where C is the censoring time)
3. The conditional probability of analysis group given the covariate vector, $\pi(a|w) = P(A = a | W = w)$ also referred to as the propensity score

The approach we consider allows for us to supply nonparametric estimators for each of the above nuisances, which could be obtained using a flexible machine learning procedure (e.g., the Super Learner). In this case, our estimator of $\Gamma^a(t)$ is fully nonparametric, and resulting inferences are valid even if one of the the nuisance parameters is not estimated well. However, it can be advantageous to also consider an approach based on parametric modeling of the nuisances in consideration of various practical issues. In particular, nonparametric estimators for the survival function can be computationally intensive and have long run times when the sample size is large; they can also be computationally unstable when the number of endpoints is small, and they can have higher variance than more parametric methods. In view of these considerations, we consider application of both parametric and nonparametric approaches for nuisance estimation.

Parametric modeling approach: We estimate the conditional survival functions η_1 and η_2 using a Cox proportional-hazards model in conjunction with the Breslow estimator for the baseline hazard. Our Cox regression models include linear terms for each covariate, and no interaction

or higher order terms (e.g., splines) unless otherwise specified. In all analyses of groups that were randomized to receive the bivalent or monovalent booster, π is estimated using the sample mean. This is valid because the treatment assignment did not depend on covariates. For other comparisons, we estimate π using logistic regression, and similarly, and we only include linear terms unless otherwise specified.

Nonparametric modeling approach: The conditional probabilities of survival and censoring are estimated using a super learner. For the survival functions η_1 and η_2 , the super learner library consists of the following estimators: (1) Kaplan-Meier estimator; (2) Cox proportional hazard estimator; (3) generalized additive models; (4) survival random forests. In all comparisons of groups that were randomized to receive the bivalent or monovalent booster, π is estimated using the sample mean. Otherwise, the propensity score is estimated using a super learner, with library: (1) the sample average of A – i.e., an intercept-only model; (2) logistic regression model; (3) generalized additive models; (4) random forests. Cross-fitting is performed in order to avoid assumptions that would disallow the use of flexible estimators that do not satisfy complexity (Donsker) conditions.

Due to the low rate of severe COVID-19, no covariate adjustment will be performed for analyses using the severe COVID-19 endpoint.

11.3.1 Primary and Secondary Analysis

In what follows, we describe our methods for covariate adjustment for the cumulative incidence approach for each of the primary and secondary analyses in Table 2. Covariate adjustment is only to be used for non-severe COVID-19 endpoints as the anticipated number of severe COVID-19 endpoints is low, and this could lead to instability of the covariate-adjusted estimates.

Parametric modeling

For all analyses comparing the monovalent and bivalent arms, we use the following variables to produce the Cox proportional hazards fit of η_1 and η_2 : recent SARS-CoV-2 infection status at Month 6 and study group.

Nonparametric modeling

For all analyses comparing the monovalent and bivalent arms, we use the following variables to produce the Cox proportional hazards fit of η_1 and η_2 : recent SARS-CoV-2 infection status at Month 6 and study group.

Main analysis vs sensitivity analysis

Of the strategies described above, the parametric modeling approach is treated as the main analysis strategy, and the nonparametric strategy is treated as a method sensitivity analysis.

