The final phase of the study, which will last until 18 months from the last enrolment, will focus on follow up for participants vaccinated with mRNA-1273 versus mRNA-1273.222, per randomization, and those with certain conditions considered at risk of prolonged SARS-CoV-2 infection (active TB, HIV with low CD4 count, and/or HIV with unsuppressed viral load). Most participants vaccinated at Month 6 prior to implementation of the bivalent vaccine (ie, all received mRNA-1273) will be exited from the trial prior to completing 12 months of follow up. The remaining participants will be administered monthly nasal swabs for nucleic acid amplification tests [NAATs] in addition to swabs initiated in response to symptoms or otherwise scheduled.

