Calendar-time-based Cox proportional hazards models will be employed to estimate the hazard ratio (HR) between the bivalent vs. monovalent randomized arms. The model will be stratified by the 4 study groups and region (RSA vs. other), thus allowing for a different baseline hazard for each of the $4 \times 2 = 8$ strata. Since the comparison is between randomized groups, the main analysis will only adjust for a small number of covariates that are deemed important or known to be associated with COVID-19 risk to increase efficiency in statistical inference. In particular, sex-assigned-at-birth (Female vs. Male) and baseline history of TB (yes vs. no) were found associated with CDC endpoints in Part A analyses, and having had a recent infection is expected to be associated with COVID-19 risk. Therefore, sex-assigned-at-birth, history of TB at Month 6, and recent SARS-CoV-2 infection status at Month 6 (see definition in Section 5) will be adjusted for in all primary and secondary analyses comparing randomized bivalent vs. monovalent boost arms. These analyses will also be repeated within people who live with HIV (PLWH) and HIV-negative participants, separately. For analyses among PLWH, CD4 counts (\leq vs. > 500 cells/mm 3 at Month 6) and HIV viral load (detectable vs. not detectable at Month 6) will be further adjusted for in

addition to sex assigned at birth, history of TB and recent infection status. For analyses among HIV-negative participants, a subset of the covariates maybe considered to avoid data sparsity, with recent SARS-CoV-2 status as the leading covariate to consider. Specifically, for Cox regression among HIV-negative participants (PLWoH), we will not adjust for TB status due to data sparsity.

We also make comparisons of covariate-adjusted cumulative incidence curves for each comparison arm. We provide a full description of the covariate-adjustment strategies in Section 11.3.

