11.3.2 Exploratory Analyses

We only use the cumulative incidence approach to address Exploratory Analyses I and II in Table 3. Other exploratory analyses (III through VII) are conducted only using the Cox modeling strategy, which is described fully in Section 11.4.3.

We now describe our covariate adjustment strategies for the cumulative incidence approach for the exploratory analyses I and II. While we considered two different covariate adjustment strategies for

the primary and secondary analyses, for the exploratory analyses, we only consider the parametric modeling strategy with binary covariates. Moreover, the same set of covariates are used as in the primary and secondary analysis.

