11.4.1 Primary analyses

Primary analysis I compares the COVE and CDC-based COVID-19 endpoints among participants randomized to a monovalent or bivalent M6 booster (RM6), counting event starting 13 days post M6 vaccination. To achieve this within a calendar-time-scale Cox regression framework, we consider the following time origin and associated analysis.

Let τ_0 denote the calendar time when the first RM6 participant completed the booster dose. For participant i , the time origin equals the number of days between 13 days after the participant's booster dose and τ_0 . At any calendar time t , the risk set consists of RM6 participants who are at least 14 days post the M6 booster. We consider the following Cox regression model:

$$\lambda_{ji}(t | A_i, W_i) = \lambda_{0j}(t) \exp \{ \beta A_i + \gamma^T W_i \} I(t > \tau_i^{D14}), \quad (4)$$

where $\lambda_{0j}(t)$ is a stratum-j-specific baseline hazard, τ_i^{D14} is Day 14 post M6 booster, $A_i = 1$ if participant i received a bivalent booster and $A_i = 0$ if a monovalent booster. When analyzing data under model (4), we will report $\exp(\beta)$ which measures the hazard ratio conditional on baseline covariates W when comparing bivalent to monovalent M6 booster.

The Cox regression will be conducted using the following stratification and covariate adjustment strategies:

- Stratification: the analysis will be stratified by 4 study groups and the geographic region (RSA or not). Therefore, a total of $4 \times 2 = 8$ strata will be considered.
- Covariate adjustment: the analysis will adjust for sex assigned at birth, history of TB, and a binary indicator of having had an infection during Part A of the study as defined in Section 7.1. The history of TB will not be adjusted in analysis restricting to PLWoH because of the small sample size.

Primary analysis II will be based on the time origin and stratification/covariate adjustment strategies as described above but restricted to the full per-protocol participants (FPP).

Primary analyses III and IV, when applicable, will be based on the same time origin as described above; however, no stratification or covariate adjustment will be conducted because of the expected small number of endpoints.

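### In the partly non-randomised FM6 cohort, the cumulative-incidence models leave out the conditions that decided which monovalent recipients stayed in follow-up

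*SAP*

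**What the plan says.** **Covariates.** SAP 11.3.1 gives the variables for the outcome and censoring models of every bivalent-monovalent comparison: "recent SARS-CoV-2 infection status at Month 6 and study group". SAP 11.3.2 covers Exploratory analyses I and II and states that "the same set of covariates are used as in the primary and secondary analysis". The propensity model, which is logistic for non-randomised comparisons (SAP 11.3), gets its covariates only through that carry-over.

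Other sections point to more. SAP 7.1 names "sex-assigned-at-birth, history of TB at Month 6, and recent SARS-CoV-2 infection status at Month 6" and, within PLWH, adds CD4 and viral load at Month 6. SAP 7.2 applies the same list to FM6 and refers to 11.3 for detail on the cumulative-incidence approach. SAP 8.2.1 says the FM6 Cox and cumulative-incidence analyses are both adjusted as for the primary and secondary analyses, and adds baseline CD4 and viral load in PLWH.

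**Follow-up.** FM6 holds every FAS participant with a Month 6 dose, inside or outside the randomisation (SAP 3). Protocol Sections 1, 2.1 and 2.1.1 say that most people given mRNA-1273 at Month 6 before the bivalent vaccine was introduced were to be exited. Those kept are the participants vaccinated per randomisation under version 6.0 and "those with certain conditions considered at risk of prolonged SARS-CoV-2 infection", namely active TB, low CD4 or unsuppressed viral load. Sites were told in January 2023.

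**Assumption.** SAP 10.1 gives as one reason for adjusting that censoring then need only be independent of failure time given arm and covariates.

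**The concern.** In FM6 the rule that ended follow-up applied to one arm only, and within that arm it depended on clinical status. Once the exits happen, the non-randomised monovalent recipients still under observation are largely those with a retention condition. Reweighting or modelling censoring can correct for this only if those conditions are among the covariates, and under 11.3.2 they are not.

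At stake are the monovalent cumulative-incidence curve after the exits and the FM6 risk difference and risk ratio. There is also a plain specification problem: two analysts following 8.2.1 and 11.3.2 in good faith would fit different models.

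**Working it through.** The plan states no figure for this point, so the check is a comparison of the sections followed by an illustration on assumed inputs.

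**Step 1. Covariates against the exit rule, FM6**

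| Place | Variables |
|---|---|
| SAP 11.3.1, carried over by 11.3.2 (cumulative incidence) | recent infection, study group |
| SAP 7.2 | list of 7.1: sex, TB history, recent infection; in PLWH also Month 6 CD4 and viral load |
| SAP 8.2.1 | as for primary and secondary analyses; in PLWH also baseline CD4 and viral load |
| SAP 11.4.3, Cox, Exploratory I | strata study group by region; sex, TB history, recent infection |
| Protocol 1, 2.1, 2.1.1 (who stays) | active TB, low CD4, unsuppressed viral load |

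Study group carries HIV status and point-of-care serostatus, so it is a partial proxy, but it holds no CD4, viral load or TB information. None of the three retention conditions is in the 11.3.2 set. The whole-cohort FM6 Cox model has TB history but no CD4 or viral load.

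**Step 2. Size at the level of the monovalent arm**

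Inputs:
- Randomised monovalent recipients: 2,000 (Protocol 6.3.1, about 4,000 at 1:1). They are not subject to the exit rule.
- Non-randomised monovalent recipients: not given. At most about 14,237 − 235 − 4,000 = 10,002 (SAP 2 and 3), before removing those who had no Month 6 dose. Range assumed: 5,000 to 10,000.
- Share with a retention condition, p = 0.15, and hazard ratio for that condition, h = 1.5 to 2: assumed.
- All non-randomised recipients without a condition exit: a simplification, since the Protocol says most.

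With hazard 1 for people without a condition, the whole-arm hazard is (1 − p) + p·h = 1.075 (h = 1.5) or 1.15 (h = 2). After the exits, with N non-randomised recipients, it is [2,000 × whole-arm hazard + 0.15·N·h] / (2,000 + 0.15·N).

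| N | h | Hazard after exits | Ratio to whole-arm hazard |
|---|---|---|---|
| 10,000 | 1.5 | (2,150 + 2,250)/3,500 = 1.257 | 1.17 |
| 10,000 | 2 | (2,300 + 3,000)/3,500 = 1.514 | 1.32 |
| 5,000 | 1.5 | (2,150 + 1,125)/2,750 = 1.191 | 1.11 |
| 5,000 | 2 | (2,300 + 1,500)/2,750 = 1.382 | 1.20 |

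The overstatement is therefore 11-32%.

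**Step 3. Effect on the risk ratio when the truth is 1.0**

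For rare events the cumulative risk ratio is close to the ratio of cumulative hazards. Take exit on day 60 (assumed) and a horizon of 165 days, the Month 12 limit in SAP 10.2. For N = 10,000 and h = 1.5 the apparent bivalent/monovalent ratio is (165 × 1.075)/(60 × 1.075 + 105 × 1.257) = 177.4/196.5 = 0.90. For h = 2 it is 189.75/228.0 = 0.83. For N = 5,000 the values are 0.94 and 0.89.

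A wider grid with N = 10,000 (p from 5% to 20%, h from 1.5 to 3, exit on day 60 or 120) gives 0.73-0.98 at day 165 and 0.68-0.94 at day 365. With h = 1 the ratio is 1.0 throughout. It is also 1.0 in expectation if the retention conditions are among the covariates and the models are correct.

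**The case against.** **The cohort is exploratory, and some of these analyses may not be run.** This stands. SAP 8.2 says the combined pre- and post-Month 6 exploratory analyses may not all be done for the primary publication.

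**Exit timing softens the Month 12 analysis.** This stands in part. The study began in December 2021, so the first participants reached Day 169 by mid-June 2022 and had about 200 days of follow-up before January 2023. People dosed around the date of version 6.0 (27 September 2022) had 96 to 126 days by January 2023. The Month 18 analysis is the more exposed.

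**The estimator tolerates a poorly estimated nuisance function (SAP 11.3).** This does not help here. That tolerance concerns estimation given the chosen covariates, and a variable missing from all three models is missing throughout.

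Four stronger readings are tempting, and the documents do not support them:

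- *A reader might infer that the shorter list is also an error in RM6 and FPP.* Those arms are randomised and the propensity is the sample mean, so no confounding follows. SAP 7.1 sets out its list in the Cox paragraph, "the analysis will adjust for sex assigned at birth, history of TB, and a binary indicator of having had an infection during Part A" repeats it for Cox in 11.4.1, and 7.1 sends the reader to 11.3 for the cumulative-incidence specification. Region enters 7.1 only as a Cox stratifier.
- *A reader might put the overstatement at 40-74%* (1.5/1.075 and 2/1.15). That compares retained with all non-randomised recipients and ignores the roughly 2,000 randomised monovalent recipients who stay in the same arm.
- *A reader might say late monovalent follow-up is mainly high-risk.* On the Step 2 inputs the high-risk share is 1,800/3,500 = 51% with N = 10,000, but 1,050/2,750 = 38% with N = 5,000.
- *A reader might say the censoring assumption fails by design, or that bivalent is bound to look better.* Both need the conditions to affect symptomatic COVID-19 hazard. Protocol 2.1 ties them to persistent or recurrent infection. SAP 7.1 says "baseline history of TB (yes vs. no) were found associated with CDC endpoints in Part A analyses" but gives no direction, and neither document links low CD4 or viraemia to the endpoint hazard.

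**Conclusion.** The point holds for Exploratory analyses I and II only. As written, the FM6 cumulative-incidence models omit known determinants of censoring in the monovalent arm, and SAP 11.3.2 does not agree with SAP 7.2 and 8.2.1.

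If active TB, low CD4 or unsuppressed viral load affect COVID-19 hazard, censoring is not independent given the stated covariates and the FM6 curves and risk ratio are biased. If they raise hazard, the bias favours bivalent. On the assumed inputs the monovalent-arm hazard after exit is overstated by about 11-32%. If they do not affect hazard, there is no bias from this source. The share with a condition, the hazard ratios, the exit times and the number of non-randomised recipients are all assumptions, so the figures show scale, not an estimate.

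No primary or secondary conclusion changes. This is a cheap improvement to an exploratory analysis.

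**What to change.** 1. Reconcile SAP 7.2 and 8.2.1 with 11.3.2, and name the covariates for each of the three models: outcome, censoring and propensity.
2. For FM6, choose one of two options:
   - Censor every pre-version 6.0 recipient at a common date tied to the January 2023 exit decision. This removes selective retention without modelling it and costs some follow-up.
   - Add TB (active TB where recorded, because retention used active TB and not history), and CD4 category and viral load at Month 6 coded within PLWH, to all three models. Keep the rule that drops adjustment when events are few.
3. Handle the whole-cohort FM6 Cox model in the same way.

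The second option raises the model from 4 terms (1 for recent infection, 3 for study group) to 7. At the five endpoints per covariate that SAP 7.1 asks of Cox models, that needs 35 events. Protocol Table 6-2 plans 75-110 events for the randomised comparison over Months 6.5 to 18, and FM6 contains that cohort. Month 12, COVE-based and HIV-negative analyses will have fewer.

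In RM6 and FPP, adding region, sex and TB history is optional, for a small gain in precision. Neither FM6 option deals with calendar period, which the study-time analysis leaves unadjusted. That is a separate matter.

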11.3.2 Exploratory Analyses

We only use the cumulative incidence approach to address Exploratory Analyses I and II in Table 3. Other exploratory analyses (III through VII) are conducted only using the Cox modeling strategy, which is described fully in Section 11.4.3.

We now describe our covariate adjustment strategies for the cumulative incidence approach for the exploratory analyses I and II. While we considered two different covariate adjustment strategies for

the primary and secondary analyses, for the exploratory analyses, we only consider the parametric modeling strategy with binary covariates. Moreover, the same set of covariates are used as in the primary and secondary analysis.

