### 6.3.1 Power calculations for coprimary objectives 1-4 (Efficacy)

Let  $VE(COVID)$  and  $VE(Severe\ COVID)$  denote vaccine efficacy of the vaccine regimen vs. counterfactual placebo among baseline SARS-CoV-2 negative participants against COVID-19 and severe COVID-19, respectively. The relative risk objectives are assessed in terms of cumulative incidence ratios between the active vaccine regimens without analysis of counterfactual placebo arms; the notations  $VE(COVID)$  and  $VE(Severe\ COVID)$  are mainly used for purposes of communicating effect sizes.

The following calculations focus on the COVID-19 endpoint because the severe COVID-19 endpoint could potentially be changed to be a secondary endpoint if there are insufficient severe COVID endpoints (Section 6.4.3). For the assessment of pre-Month 6 stage objectives, sample sizes of Groups 1 and 2 in the FAS are considered. For the assessment of post-Month 6 stage objectives, the following calculations consider approximately 4000 participants in Groups 1-4 received their Month 6 vaccination (mRNA-1273 vs. mRNA-1273.222) per randomization under protocol version 6. This sample size is consistent with study data as of June 2023. As shown in the upper portion (pre-Month 6 stage) of Table 6-2, there is ample power ( $> 90\%$ ) to detect a relative risk of 2.0 between Groups 1 and 2 against the null hypothesis  $H_0: RR = 1.0$  during Month 0 and 6 in the pre-Month 6 stage. In reality, the sample sizes of the PLWH hybrid immunity group who receive 1 pre-Month 6 dose and the PLWH pure vaccine group who receive 2 pre-Month 6 doses are likely smaller than the sample sizes of Groups 1 and 2, respectively. As shown in the lower portion (post-Month 6 stage) of Table 6-2, when the annual incidence of the primary endpoint is in the range of 2.5%- 3.5% in the mRNA-1273 arm, there is approximately 80-90% power to detect a relative risk of 2.0 – 2.5 between mRNA-1273 vs. mRNA-1273.222 vaccination during Month 6.5 and 18 in the post-Month 6 stage.

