These calculations are carried out assuming 5% annual dropout, 5% probability of missing any of the 3 doses, VE(COVID) of 63% between Month 0 and Month 6 in Group 1 (SARs-CoV-2 negative) and in Group 2, and 5% six-month COVID-19 incidence rate among unvaccinated PLWH SARs-CoV-2 negative individuals in the community. The assumption on VE(COVID) of 63% between Month 0 and Month 6 accounts for a possible reduced protection of the vaccine regimen in PLWH against the SARS-CoV-2 variant at the time of the trial conduct. The 5% six-month background incidence rate assumption was based on the observed 4.7%, 5.25%, and 10.38% placebo arm six-month incidence rates among baseline SARS-CoV-2 negative participants in, respectively, the AstraZeneca phase 3 (149), Novavax phase 2 (107), and Janssen ENSEMBLE phase 3 (28) trials restricted to South African study sites, and building in conservative margin given the availability of vaccines to potentially reduce transmission and infection in the region. The background SARS-CoV-2 (re-infection) incidence rate among unvaccinated PLWH SARS-CoV-2 positive individuals in the community is assumed to be half of that of unvaccinated PLWH SARS-CoV-2 negative individuals based on the reported protection of approximately 55% against the Omicron variant from previous SARS-CoV-2 infection in South Africa (150-152) and in other countries (153). The statistical power is calculated using an exact binomial test with a (two-sided) false positive error rate of 0.05.

**Table 6-2 Pre-Month 6 stage:** power to detect relative risk (Months 0-6) being different from 1.0 between Group 1 (n=4200) and Group 2 (n=8400).

True VE (0-6) of Group 1 (n=4200)	Relative Risk (Groups 1 vs. 2)	Total expected number of events M0-6	Power
60%	1.3	189	45%
	1.6	176	85%
	2.0	167	99%
70%	1.2	149	17%
	1.5	135	59%
	2.0	125	96%
70%	1/1.3	207	45%
75%	1/1.6	203	85%
80%	1/2.0	200	99%
75%	1/1.2	159	17%
80%	1/1.5	153	59%
85%	1/2.0	150	96%

**Post-Month 6 stage:** power to detect relative risk (Months 6.5-18) being different from 1.0 between mRNA-1273 vs. mRNA-1273.222 Month 6 vaccination (n=4000, 2000 vs. 2000),.

Annual incidence for mRNA-1273 Month 6 vaccination arm	Relative Risk (mRNA-1273 vs. mRNA-1273.222)	Total expected number of events M6.5-18	Power
3.5%	1.5	110	54%
	2.0	106	93%
3.0%	2.0	91	87%
	2.5	90	99%
2.5%	2.0	76	78%
	2.5	75	96%

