The Ubuntu study enrolled a total of 14,237 participants into 4 study groups based on their baseline HIV serostatus (positive or negative) and anti-spoke SARS-CoV-2 Point-of-Care serology (POCS) status (positive or negative). Prior to protocol version 6.0, for Part A of the study, participants were assigned to receive 1 dose (Month 0), or 2 doses (Month 0 and Month 1) of mRNA-1273 based on their baseline POCS result being positive or negative, respectively. Prior to protocol version 6.0, for Part B of the study, randomization code was generated but all participants received the monovalent mRNA-1273 vaccine at Month 6 due to the bivalent vaccine not being available at the time, and no randomization assignment was actually performed. At the time of implementation of protocol version 6.0 after the bivalent vaccine became available, The Ubuntu study enrolled a total of 14,237 participants into 4 study groups based on their baseline HIV serostatus (positive or negative) and anti-spoke SARS-CoV-2 Point-of-Care serology (POCS) status (positive or negative). Prior to protocol version 6.0, for Part A of the study, participants were assigned to receive 1 dose (Month 0), or 2 doses (Month 0 and Month 1) of mRNA-1273 based on their baseline POCS result being positive or negative, respectively. Prior to protocol version 6.0, for Part B of the study, randomization code was generated but all participants received the monovalent mRNA-1273 vaccine at Month 6 due to the bivalent vaccine not being available at the time, and no randomization assignment was actually performed. At the time of implementation of protocol version 6.0 after the bivalent mRNA-1273.222 vaccine became available, the previous randomization code was replaced with the randomization code generated under an updated randomization plan, ensuring that the treatment number assigned at original “randomization” was kept and corresponded to either mRNA-1273 or mRNA-1273.222. This allowed the site to use the randomized assignment to define the Month 6 vaccination for participants receiving the Month 6 vaccination under protocol version 6.0. An updated treatment key was provided to sites with participants who re-consented on protocol version 6.0, for documenting the Month 6 vaccinations only. Only as many treatment assignments as

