For all primary and secondary comparisons and a subset of exploratory analyses, the time origin for time-to-event COVID-19 or severe COVID-19 endpoints is either the day of or 13 days after the Month 6 vaccination visit, counting events either starting 1 day or 14 days after the Month 6 vaccination. For a subset of exploratory analyses that will include information from enrollment until Month 12 or Month 18, the time origin is either the date of enrollment or 13 days after the Month 6 vaccination visit, counting events either starting 1 day after enrolment or 14 days after the Month 6 vaccination. The Cox model approach will always use the calendar time scale and the cumulative incidence approach will always use the study time scale. See more details about these two approaches in later sections. These analyses will address the co-primary objectives, key secondary objectives and exploratory objectives specified in the protocol (Version 8.0).

Different analyses specify different time origins for the COVID-19 or severe COVID-19 (if applicable) time-to-event T ; the endpoint date is always the same: the date of the first occurrence of COVID-19 or severe COVID-19 endpoint after the corresponding time-origin and up to the date of Month 12 or Month 18 visit. The failure time T is right-censored by the first event of receipt

of outside vaccination, loss to follow-up, or reaching the upper window of the Month 12 (for the Month 12 analyses) or Month 18 visit (for the final analyses), whichever occurs first.

5 SARS-CoV-2 status at baseline and at Month 6

This section defines baseline and Month 6 SARS-CoV-2 statuses, as well as recent SARS-CoV-2 infection status at Month 6 for the pre- & post-M6 stage combined analyses and for the post-M6 stage analyses. These variables will be used as a stratification variable to define different analysis groups, evaluated as a covariate to adjust for prior exposure, and/or as a potential effect modifier in various analyses.

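### The exploratory FM6 cumulative-incidence contrast (SAP 11.3.2) runs on study time with no calendar term, so it confounds bivalent versus monovalent with epidemic period

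*SAP*

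**What the plan says.** FM6 (SAP section 3) contains every FAS participant who had a Month 6 dose, randomised or not. Before Version 6, SAP section 2 says, "all participants received the monovalent mRNA-1273 vaccine at Month 6 due to the bivalent vaccine not being available at the time". The bivalent group in FM6 is therefore entirely randomised and later in calendar time, while the monovalent group mixes randomised recipients with earlier ones.

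For this cohort SAP 11.3.2 says "We only use the cumulative incidence approach to address Exploratory Analyses I and II in Table 3", in its parametric form, and that "the same set of covariates are used as in the primary and secondary analysis". In SAP 11.3.1 that set is recent infection status at Month 6 and study group. SAP 7.2 instead points back to the list in 7.1 (sex, TB history, recent infection). Neither list contains calendar date. On the time scale, SAP section 4 says "the cumulative incidence approach will always use the study time scale".

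SAP 11.3 specifies an outcome model, a censoring model and, for non-randomised comparisons, a logistic propensity model. SAP 11.2 attaches confidence intervals and two-sided p-values. SAP 10.1 allows the FM6 contrasts to be read as average treatment effects if the usual identification assumptions hold. SAP 7.2, 8.2.1 and 11.4.3 also plan a Cox model, on calendar time and stratified by study group and region, for the same comparison.

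On follow-up, the Protocol Overview says "Most participants vaccinated at Month 6 prior to implementation of the bivalent vaccine (ie, all received mRNA-1273) will be exited from the trial" before completing 12 months. Those with active TB, low CD4 count or unsuppressed viral load stay, and Appendix J keeps participants who are still testing positive. Those who remain get monthly swabs.

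**The concern.** Nobody dosed before Version 6 could receive bivalent, so calendar period is tied to arm. On study time, day 60 after an early monovalent dose and day 60 after a later bivalent dose fall in different parts of the epidemic. The method treats them as comparable once recent infection and study group are accounted for. SAP 10.3 itself says the epidemic changes unpredictably over calendar time, and SAP 11.4 credits the calendar-time Cox model with handling that.

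Ascertainment differs too. The CDC-based definition, which SAP 6.1 makes the leading one, accepts a positive NAAT that symptoms did not trigger (SAP 6.1.2), so the later monthly swabs can find more cases. The COVE-based endpoint is symptom-triggered and much less exposed to this.

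At stake is an FM6 risk ratio, with p-value and conditional causal reading, printed beside the randomised result. It could appear to reinforce or contradict that result through calendar period alone.

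**Working it through.** **Reproducing the plan's figures.** Protocol 6.3.1: "The statistical power is calculated using an exact binomial test with a (two-sided) false positive error rate of 0.05"; "the following calculations consider approximately 4000 participants in Groups 1-4 received their Month 6 vaccination" under Version 6, split 2,000 and 2,000; and power is given "when the annual incidence of the primary endpoint is in the range of 2.5%- 3.5% in the mRNA-1273 arm". With equal arms and D events in total, events in the monovalent arm are binomial(D, p) with p = RR/(1+RR), tested against 0.5 with equal tails. Using the D values in Table 6-2, the six post-Month 6 rows give 54.1, 92.9, 87.4, 98.7, 78.1 and 96.2%, against the stated 54, 93, 87, 99, 78 and 96%. All six reproduce, so 4,000 recipients and a rate of 3% per year are fair planning inputs.

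**Inputs for the bias.**
- FAS: 14,237 − 235 = 14,002 (SAP sections 2 and 3).
- Scenario A: 4,000 dosed under Version 6. Assume 95% of FAS had a Month 6 dose, borrowing the 5% missed-dose assumption in Protocol 6.3.1: 0.95 × 14,002 − 4,000 = 9,302 before Version 6.
- Scenario B: 80% dosed under Version 6, the share assumed in Protocol 6.3.2, and the rest before: 0.8 × 14,002 = 11,202 and 2,800.
- k, the incidence in the earlier period divided by that in the later: not in the documents. Range taken: 1/3 to 3.

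**Closed form, no overlap in follow-up.** Let w be the pre-Version 6 share of the monovalent group. For identical vaccines, apparent bivalent/monovalent RR = 1/(wk + 1 − w).
- A: w = 9,302/(9,302 + 2,000) = 0.823. At k = 1/2, 1/(0.4115 + 0.177) = 1.70; at k = 2, 1/(1.646 + 0.177) = 0.55.
- B: w = 2,800/(2,800 + 5,601) = 0.333. At k = 1/2, 1.20; at k = 2, 0.75.

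**Null simulation with overlapping follow-up.** Assumed: pre-Version 6 doses spread over 150 days and Version 6 doses over the next 150; 3% per year after the switch and k times that before; 5% annual dropout; no exits; 200 runs per row. The horizon is 165 days, the Month 12 value in SAP 10.2. The study-time estimate is a Kaplan-Meier risk ratio without covariates. The comparator is a Mantel-Haenszel rate ratio in 14-day calendar strata, standing in for calendar-time Cox. Percentages are rejections at nominal 5%.

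| k | A, no overlap | A, simulated, study time | A, simulated, calendar strata | B, no overlap | B, simulated, study time |
|---|---|---|---|---|---|
| 1/3 | 2.22 | 1.29 (22%) | 0.97 (7%) | 1.29 | 1.12 (12%) |
| 1/2 | 1.70 | 1.24 (18%) | 1.01 (4.5%) | 1.20 | 1.08 (3.5%) |
| 1 | 1.00 | 0.97 (4%) | 0.97 (5.5%) | 1.00 | 1.00 (5%) |
| 2 | 0.55 | 0.71 (36.5%) | 0.98 (4%) | 0.75 | 0.87 (12.5%) |
| 3 | 0.38 | 0.56 (86.5%) | 0.97 (4%) | 0.60 | 0.77 (45.5%) |

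The k = 1 row of scenario A shows simulation noise of about 0.03.

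**Exits alone (scenario A, k = 1, exits from day 225 over 60 days).** With 10 to 20% retained at 1.5 to 3 times the risk, the study-time RR at 165 days is 0.96 to 0.99, with 3 to 5% rejection. At about 350 days, with 15% retained at twice the risk, it is 0.91 with 11% rejection.

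**Period and exits together (15% retained at twice the risk).** At 165 days the RR is 1.16 at k = 1/2 and 0.71 at k = 2. At about 350 days it is 0.97 and 0.77, so the two biases can partly cancel. In the 350-day runs the calendar-stratified estimate, which had no TB, CD4 or viral-load terms, was still 0.86 to 0.88.

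**The case against.** The SAP already guards against much of this. It says the FM6 comparison is not a randomised one, labels it exploratory, warns in 8.2 that not all such analyses may appear in the primary publication, makes the causal reading conditional, and plans a calendar-time Cox model for the same contrast. All of that stands and limits the weight of the point. It does not justify keeping a second inferential method that lacks the calendar protection.

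Three stronger readings are tempting and are not supported.
- A reader might infer that outcome-related exits are ignored and drive the distortion. A censoring model is specified in SAP 11.3. Its weakness is that the 11.3.1 covariates omit TB, CD4 and viral load, which decide who stays. Whether TB is really omitted depends on whether 7.2 or 11.3.1 governs. Moreover, retention turns on active TB, whereas SAP 7.1 reports an association with TB history. Exits alone gave little bias at Month 12.
- A reader might take the 11.3.2 sentence to mean that Exploratory I and II rest on cumulative incidence alone. It means that, among the exploratory analyses, only these two use that method. The Cox model covers them too and, in the pooled cohort, already adjusts for TB history (SAP 11.4.1 to 11.4.3).
- A reader might take the no-overlap ratios as the expected size. Version 6 is dated September 2022 and the follow-up change was communicated in January 2023, so some overlap is likely and the simulated figures are the fairer guide.

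One could also add vaccination date to the models. Because the chance of bivalent was zero before Version 6, that breaks positivity, and restricting to dates when both vaccines were given essentially returns RM6.

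**Conclusion.** The point holds for the FM6 cumulative-incidence contrast in Exploratory Analyses I and II. Under scenario A with overlapping follow-up, a two-fold difference in incidence between periods makes identical vaccines show an RR of about 1.24 or 0.71, with 18 to 37% false rejection. Under scenario B the corresponding figures are 1.08 and 0.87. Scenario A deserves more weight, because Protocol 6.3.1 says about 4,000 matches study data as of June 2023.

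These sizes rest on an assumed number of pre-Version 6 recipients, an assumed period ratio and assumed dates. The simulation also omits the two planned covariates. Recent infection at Month 6 describes the past, not later exposure, so it is unlikely to stand in for calendar period.

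Selective exit is secondary: negligible at Month 12 and modest at Month 18. A reader might extend the concern to the main result; the RM6 and FPP comparisons are between concurrently randomised arms and are not affected. This is a cheap improvement to an exploratory analysis, not a threat to the trial's conclusions.

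**What to change.** - In SAP 11.2 and 11.3.2, with matching edits in 7.2, 8.2.1 and 10.1, drop the cumulative-incidence contrasts and tests for FM6 and make the planned calendar-time Cox model the only FM6 inference.
- If FM6 incidence curves are still shown, label them descriptive, with no p-value and no causal reading.
- In SAP section 4, name sponsor-directed exit as a censoring event.
- Reconcile the covariate list in 7.2 (which refers to 7.1) with the one in 11.3.1 and 11.3.2.
- Note as a limitation that the Month 18 FM6 Cox result may keep some bias from selective exit. The PLWH analysis already adjusts for CD4 and viral load; the pooled one does not.

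The cost is SAP wording and slightly less work. What is lost is an inferential absolute-risk contrast in FM6; RM6 and FPP still supply one between randomised arms.
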